# 5. Treatment of Participants

#### 5.1 Introduction

This trial is a cross-over study of a control arm (threshold of ≤90 g/L) vs an intervention arm (threshold of ≤70 g/L). Participants will be randomised to be in one arm for their first cycle of treatment and the other arm for the second cycle of treatment. The arms are described in the sections below. The trial will compare two different policies for RBC transfusion, "restrictive" and "liberal". All recruited participants at a participating site should be transfused in accordance with the randomised transfusion policy for that cycle of treatment. Any transfusion required as part of the policy should be commenced within 24 hours of obtaining the haemoglobin result for inpatients and 72 hours for outpatients.

Prior to commencement of allocated transfusion policy in cycle 1, patients may receive red cell transfusions according to clinical need. This recognises the challenge of approaching and consenting patients at the time of new diagnosis and the importance of allowing patients and staff a short period of time to fully consider the trial. During this run-in period, red cell transfusion policies will be consistent with local guidelines, and typically at haemoglobin thresholds of 80g/L.

[figure not shown]
Allocation to either the restrictive or liberal policy will then apply from at or before Day 5 onwards in cycle 1. For cycle 2 chemotherapy treatment, participants will follow the alternative transfusion policy (ie if allocated to 'restrictive' arm for cycle 1, this would be the 'liberal' arm for cycle 2).

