# 5.2 Intervention Arm: Restrictive Transfusion Policy (RBCs transfused when haemoglobin ≤70g/L)

Following enrolment, the haemoglobin values of participants will be recorded according to routine clinical care. If the haemoglobin value is recorded as ≤70 g/L, red blood cells should be transfused at a dose of 1 unit at a time, with the aim of keeping the haemoglobin range between 71-80 g/L. The timing of repeat haemoglobin measurements should be decided by the attending haematologist. Further red blood cell transfusions should only be administered if the haemoglobin value decreases to a value of 70g/L or less (see figure 1). Any transfusion required as part of the policy should be administered within 24 hours of obtaining the haemoglobin result (up to 72 hours for outpatients). For participants with haemoglobin values significantly lower than the threshold (i.e. where one unit would not be expected to increase the haemoglobin level into the desired range) more than 1 unit at a time may be transfused.

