# 5.3 Control Arm: Liberal Transfusion Policy (RBCs transfused when haemoglobin ≤90g/L)

Following enrolment, the haemoglobin values of participants will be recorded according to routine clinical care. If the haemoglobin value is recorded as ≤90 g/L, red blood cells should be transfused at a dose of 1 unit with the aim of keeping the haemoglobin range between 91-100 g/L. The timing of repeat haemoglobin measurements should be decided by the attending haematologist. Further red blood cell transfusions should only be administered if the haemoglobin value decreases to a value of 90g/L or less (see figure 2). Any transfusion required as part of the policy should be administered within 24 hours of obtaining the haemoglobin result (or 72 hours for outpatients). For participants with haemoglobin values significantly lower than the threshold (i.e. where one unit would not be expected to increase the haemoglobin level into the desired range), more than 1 unit at a time may be transfused.

[figure not shown]

Figure 2: Control Arm: Liberal transfusion strategy

\*or 2 units for outpatients at clinician's discretion

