#### 9.2.2 Secondary Outcomes

Overall haemoglobin difference: mean haemoglobin for the liberal and restrictive strategies using all haemoglobins reported.

**Adherence:** These will be measured by determining:

- The proportion of enrolled participants for whom the transfusion policy was successfully followed until the end of that chemotherapy cycle/death, whichever comes first. The transfusion policy will be defined as having been successfully followed if the participant always received a RBC transfusion within the defined time frame when their haemoglobin dropped below the trigger level, and did not receive any RBC transfusions when their haemoglobin was above the trigger level.
- The proportion of enrolled participants for whom the transfusion policy was successfully followed but allowing for one 'violation'.
- The proportion of transfusions per participant that were correctly given according to their haemoglobin trigger (i.e. had a haemoglobin value ≤70 g/L in the restrictive transfusion group and a haemoglobin value ≤90 g/L in the liberal transfusion group).
- The proportion of times a participant received a transfusion contrary to their haemoglobin trigger (i.e. had a haemoglobin value >70 g/L in the restrictive transfusion group and a haemoglobin value >90 g/L in the liberal transfusion group).
- The overall proportion of transfusions that were correctly given according to the participant's haemoglobin trigger (i.e. had a haemoglobin value ≤70 g/L in the restrictive transfusion group and an haemoglobin value less than ≤90 g/L in the liberal transfusion group).
- The overall proportion of times a transfusion was given contrary to the participant's haemoglobin trigger (i.e. had a haemoglobin value >70 g/L in the restrictive transfusion group and an haemoglobin value >90 g/L in the liberal transfusion group).

- The overall proportion of transfusions that were given correctly according to the participant's haemoglobin trigger by whether given as inpatient or outpatient
- The proportion of inpatient and outpatient transfusions given as single or multiple unit transfusions
- Percentages of transfusions performed where the pre-transfusion haemoglobin concentrations fell below, within and above the target haemoglobin range
- Percentages of transfusions performed where the post-transfusion haemoglobin concentrations fell below, within and above the target haemoglobin range

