- **Recruitment rate:** the proportion of eligible participants enrolled will be summarised, along with the number of replaced participants and participant tolerability by transfusion strategy **and reasons for withdrawing early from the study.**
- Red Blood Cell Exposure: The difference in number of red blood cell units administered will be compared between the intervention groups up to death/end of chemotherapy cycle (whichever comes first).
- QoL questionnaire compliance: this will be summarised by treatment strategy and timepoint

Protocol adherence will be measured over time, to determine if adherence rates improve. Adherence rates will also be compared between transfusion arms and between sites. Transfusions will only be viewed as having successfully followed the transfusion policy if they are given within the pre-defined time period of 24 hours after a participant's haemoglobin has dropped below the trigger level. **Key** clinical characteristics of **recruited participants will be compared against** patients recruited to **the** AML 18 and 19 trials (in order to give a measure of patients excluded from this feasibility study which may be attributed to physician discretion).

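### Section 9.2.2 scores transfusion adherence on a 24-hour limit, while sections 5.1 to 5.3 allow outpatients 72 hours, so outpatient transfusions at 24 to 72 hours follow the policy but count as non-adherent

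*Protocol*

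**What the plan says.** The treatment sections set the time limit by care setting. Protocol section 5.1 requires a policy transfusion to be "commenced within 24 hours of obtaining the haemoglobin result for inpatients and 72 hours for outpatients". Section 5.2 (restrictive arm) has it "administered within 24 hours of obtaining the haemoglobin result (up to 72 hours for outpatients"), and section 5.3 (liberal arm) likewise gives 24 hours "or 72 hours for outpatients".

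Section 9.2.2 sets the scoring. After the list of adherence outcomes, it says that transfusions will be viewed as having "successfully followed the transfusion policy if they are given within the pre-defined time period of 24 hours", counted from when the haemoglobin fell below the trigger. The sentence is worded as an exclusive condition and does not mention outpatients. Nothing else in section 9 brings back the 72-hour allowance.

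Outpatients are in scope. The synopsis lists them in the setting, section 5.4 applies the policy to them as far as possible, and one adherence bullet in 9.2.2 splits transfusions "by whether given as inpatient or outpatient".

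**The concern.** A site is told one limit for treating outpatients and is scored against a shorter one. Any outpatient transfusion given after 24 hours and by 72 hours is a success under section 5 and a failure under section 9.2.2. The recorded failure comes from the scoring rule and says nothing about clinician behaviour.

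This matters because the trial's hypothesis is that adherence is achievable, and 9.2.2 plans to follow adherence over time and compare it between arms and sites. A site that treats more patients as outpatients could look less adherent with no real difference in conduct. Section 6.2.6.1 wants to learn whether local systems affect adherence, and this artefact would be mixed into that question.

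**Working it through.** The protocol gives no adherence figure to reproduce, and the sample-size calculation in section 9.3 does not use transfusion timing. The check is therefore a comparison of text, followed by an illustration.

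**Step 1. The rules side by side**

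| Place | Inpatient limit | Outpatient limit | Clock starts | Act timed |
|---|---|---|---|---|
| 5.1 | 24 h | 72 h | result obtained | commenced |
| 5.2 | 24 h | 72 h | result obtained | administered |
| 5.3 | 24 h | 72 h | result obtained | administered |
| 9.2.2 scoring sentence | 24 h | 24 h (no exception) | haemoglobin has fallen below trigger | given |

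The outpatient limit differs. So does the wording of the clock start, and section 5 itself uses two verbs for the act being timed.

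**Step 2. Which transfusions are misclassified**

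- Inpatient, any time: the same limit in both places, so no conflict in the window.
- Outpatient, within 24 h: adherent in both.
- Outpatient, after 24 h and up to 72 h: adherent in section 5, non-adherent in 9.2.2.
- Outpatient, after 72 h: non-adherent in both.

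Only the third group is affected.

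**Step 3. Which outcomes the time rule reaches**

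- *Comparisons over time, between arms and between sites (9.2.2):* reached, as they stand in the same paragraph as the 24-hour sentence.
- *Participant-level outcome (policy followed throughout) and the version tolerating one violation (9.2.2):* reached only if 24 hours is the time frame meant. The bullet refers to a defined time frame but gives no hours, so it could equally point to section 5.
- *Transfusion-level bullets, including the inpatient/outpatient split (9.2.2):* not reached on their wording, which rests on the haemoglobin trigger alone.
- *Primary outcomes (9.2.1):* not reached. Both use pre-transfusion haemoglobin.
- *Feasibility criterion of at least 70% in both arms (9.4):* not reached. It uses haemoglobin relative to the target range.

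**Step 4. Illustration of size**

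Let s be the share of transfusions given to outpatients and f the share of those given at 24 to 72 hours. The protocol states neither, so all values below are assumed. A site that follows section 5 perfectly scores 1 − s × f on a transfusion-level measure using the 24-hour rule:

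- s = 10%, f = 25%: 1 − 0.10 × 0.25 = 97.5%
- s = 20%, f = 50%: 1 − 0.20 × 0.50 = 90%
- s = 30%, f = 50%: 1 − 0.30 × 0.50 = 85%

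If the participant-level outcomes also use 24 hours, one permitted outpatient delay within a cycle turns a fully adherent participant into a failure, and two exceed the one-violation allowance.

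**The case against.** The strongest reply is that little of consequence depends on this sentence. The affected measures are secondary, the trial is a feasibility study, and section 5.4 intends mainly inpatient stays, so few transfusions may fall in the disputed interval. That stands, and it limits the size. It does not remove the contradiction.

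A second reply is that the SAP may apply the right window. It may, but the protocol does not leave the point open: it states a specific rule that conflicts with its own policy. The amendment history says version 2.0 was issued to clarify section 9 and align it with the SAP, and the 24-hour sentence stands in that version.

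A reader might draw four stronger conclusions that the protocol does not support:

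- *That the 70% criterion or a primary outcome is at risk.* Neither uses time to transfusion.
- *That the inpatient/outpatient split is biased.* That bullet counts transfusions by the haemoglobin trigger, with no time element in its wording.
- *That the liberal arm is penalised more, because 90 g/L may be reached more often after discharge.* This is conjecture; no figure or passage supports a direction.
- *That measured adherence could fall by as much as 30 points.* That needs, for example, 40% outpatient transfusions with 75% of them at 24 to 72 hours (0.40 × 0.75 = 30%), which fits poorly with mainly inpatient stays.

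Nor does the participant-level bullet itself contradict section 5. It gives no hours and is merely open to either reading.

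**Conclusion.** The scoring rule is wrong as written. It cannot be applied alongside sections 5.1 to 5.3 without marking some policy-compliant outpatient transfusions as failures. The error is certain for outpatient transfusions at 24 to 72 hours within the time-based comparisons, and conditional for the two participant-level outcomes. The decision to proceed to a larger trial, as section 9.4 defines it, is not affected.

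The size is unknown. The scores of 97.5%, 90% and 85% rest wholly on assumed values of s and f and show only how the artefact scales; they are not forecasts. The direction between arms is also unknown. This should be corrected because it is cheap to do so and adherence is what the study sets out to measure, but it is not a threat to the main result.

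**What to change.** Reconcile the scoring sentence in section 9.2.2 with sections 5.1, 5.2 and 5.3. Three things need to be settled:

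1. Adherence is scored against the same window, by inpatient or outpatient setting, that the policy gives clinicians.
2. The clock starts at the same event in both places (haemoglobin result obtained, or haemoglobin fallen below the trigger), and one term is used for the act being timed.
3. The text says which adherence outcomes the time rule governs, in particular whether it is the time frame meant in the participant-level bullet and whether the bullets based on the haemoglobin trigger stay free of it.

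The choice of window is a clinical matter for the sponsor and investigators; the statistical need is only that policy and scoring agree.

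The cost is a small edit to 9.2.2 and a matching derivation in the SAP, with no additional patients. The case report form is not available here, so the sponsor should confirm that the recorded times and care setting are enough to apply the agreed rule.

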#### 9.2.3 Clinical Outcomes

- Death: All-cause mortality at 3 months post study completion
- **Bleeding**: Clinically significant bleeding events are defined as equivalent to WHO Grade 3 or 4. These events will be captured using definitions applied for bleeding assessments conducted using a tool based upon that used in the TOPPS trial and further developed by an international working group the BEST collaborative.
- Proportion of participants experiencing thromboembolic and ischaemic events:
   Includes myocardial infarction, stroke, pulmonary embolus, clinically overt and line-related thrombotic events. Line related blockage may have other causes related to the type of line used. (These thromboembolic and ischaemic events may be related to higher haemoglobin concentrations, although MI may occur more commonly with lower thresholds)
- Syncopal events
- Transfusion reactions
- Length of hospital stay
- Proportion of participants with at least one blood culture verified bacterial infection

- Median EQ-5D-5L Visual Analogue Scale score for symptomatic and nonsymptomatic transfusions
- Health related quality of life at baseline, middle and end of each cycle using EQ-5D-5L/ EORTC QLQ C30 forms)

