	alternative transfusion policy (i.e. if allocated to restrictive arm for cycle 1, this would be the liberal arm for cycle 2
Study hypothesis	It is feasible to achieve adherence when randomising patients to one of 2 haemoglobin thresholds and maintaining haemoglobin concentrations between either 71-80 g/L or 91-100 g/L
Primary outcome measure(s)	
 
Percentage of pre-transfusion haemoglobin concentrations being below the target range of the assigned red cell transfusion strategy
 
Achievement of at least a 15g/L difference between the mean pre-transfusion haemoglobins in the two transfusion groups
 

Secondary outcome measure (s)	Adherence outcomes: transfusions given per protocol, red cell exposure, adherence to outcome monitoring, recruitment rate, characteristics of recruited participants  Clinical outcomes: bleeding, thrombosis, culture verified bacterial infections, platelet transfusion, Quality of Life (QoL), transfusion reactions, death  Monitoring outcomes: compliance with data collection between sites
Duration of Study	
 
Recruitment for 18 months
 
Intervention from diagnosis until end of second cycle or cycle 2 Day +42 i.e. the 42nd day after the last dose of chemotherapy (approximately 3 months)
 
No further follow-up beyond intervention period
 
Duration of trial – 2 years
 

Study Schedule	The study schedule can be found in section 6.1 of the protocol.
Sample Size	36 patients (for one complete cycle of chemotherapy) with equal numbers in each arm
Ancillary Studies/substudies	None
Trial manager	[name]
CTU Project Manager	[name]

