#### 1.4 Justification for choice of thresholds and trial design summary

Participants will participate in the study for the first two cycles of chemotherapy. The haemoglobin threshold for the first cycle will be randomised and the participant will cross over to the other threshold for the second cycle. The two primary outcomes of the feasibility trial will be measures of adherence to protocol and achievement of a difference in mean pretransfusion haemoglobin levels. Participants will be followed from randomisation until the end of the second cycle of intensive chemotherapy.

The thresholds for this feasibility trial were informed by the results of the survey and audits described in section 1.2. The thresholds reflect a common current haemoglobin threshold at (just under) 80g/L, and a need to test two policies around this standard with a likelihood of achieving clinically meaningful separation between the groups.

A cross-over trial design allows each participant to act as their own control, reducing the possibility of any observed difference being due to patient-related confounding factors. It may reduce the amount of variability observed in the outcome measures of interest, and be more statistically 'efficient', and reduces the number of patients required to detect a difference.

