#### 4. Randomisation

#### 4.1 Randomisation practicalities and blinding

Patients at each site will be randomised using an online randomisation system at sealedenvelope.com. The randomisation number will be recorded on the CRF. Patients will be randomised in a ratio of 1:1 to either the control arm (threshold of  $\leq$ 90 g/L) or the intervention arm (threshold of  $\leq$ 70 g/L) for their first cycle of treatment. The patient will cross-over to the other arm for their second cycle of treatment.

The person on the trial team responsible for undertaking the randomisation procedure will not be the same person who gained consent from the patient.

The participant blinding to the trial allocation arm will be tested with a simple directed question asking which treatment arm the participant considers they are allocated to at each study visit.

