#### 5.7.2 Duration of study/end of study

The randomised transfusion policies will be followed for all eligible participants up to the end of each course of chemotherapy, for two consecutive cycles. For eligible participants, the day of randomisation is defined as (Cycle 1) Day 1 (which must be at or before Day 5 from start of chemotherapy) and the transfusion policies will be followed to the end of the second cycle of intensive chemotherapy (or death). Data collection will occur up to the end of each cycle (day +42 or the start of the next cycle) and follow up QoL assessment will take place at the end of each cycle, i.e. at admission or attendance for commencement of the next cycle of treatment. In the event that no subsequent cycle of treatment is given, participants will be contacted at day +42.

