#### 6.8 Trial Closure

The trial will be closed when all participants have been recruited and have completed the trial intervention period.

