The mean EQ-5D-5L and EORTC QLQ C30 scores for each arm will be calculated and compared at baseline and after each chemotherapy cycle. Clinically meaningful improvement will be defined as ≥0.08 on the calculated health utility EuroQOL-5D score and ≥10 points on the EORTC QLQ-C30 score (for all scores apart from fatigue and dyspnoea, for which an improvement is ≤-10). In addition to aggregate data, the percentages of participants individually achieving a clinically meaningful improvement, at any time point, compared to the baseline score (the first QoL questionnaire at randomisation), in each of the two strategies will be compared.

For other and safety analyses, data from all randomised subjects will be evaluated and descriptive statistics presented. Key clinical characteristics of enrolled participants will be compared against all recruits to AML 18 and 19 trials. The extent of exposure will be summarised (median RBC and platelet units transfused during each chemotherapy course), as well as the clinical course, such as interval between transfusions and transfusion reactions. The incidence of WHO Grade 3 or 4 bleeding and death will be summarised by treatment strategy, and length of hospital stay compared. Comparisons will be made between the two haemoglobin concentration threshold transfusion strategies. Any adverse events potentially related to the transfusion threshold such as cardiac ischaemic events, congestive heart failure, strokes (cerebrovascular accidents, CVA), thromboembolic or syncopal events, will be summarised and compared between the two arms.

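### The mortality outcome falls three months after the protocol's own follow-up ends, and deaths after cycle 2 cannot be assigned to a single transfusion strategy

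*Protocol*

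**What the plan says.** **When mortality is measured.** Section 9.2.3 (Clinical Outcomes) gives the only definition of the death outcome: "All-cause mortality at 3 months post" study completion.

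**When follow-up ends.** Four other places set an earlier end:
- Study Synopsis, Duration of Study: "No further follow-up beyond intervention period". The same cell describes the intervention as "Intervention from diagnosis until end of second cycle or cycle 2 Day +42", which it puts at approximately 3 months.
- Section 1.4: "Participants will be followed from randomisation until the end of the second cycle of intensive chemotherapy".
- Section 5.7.2: "Data collection will occur up to the end of each cycle (day +42 or the start of the next cycle"). If no further cycle is given, the participant is contacted at day +42.
- Section 6.8: "The trial will be closed when all participants have been recruited and have completed the trial intervention period".

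Table 1 in section 6.1 has a Death row, ticked only under a column headed 3 Months. The table does not say from what date the 3 months run.

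**How death is analysed.** Section 9.4: "The incidence of WHO Grade 3 or 4 bleeding and death will be summarised by treatment strategy". It gives no time window. On the design, section 4.1 says: "The patient will cross-over to the other arm for their second cycle of treatment".

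**The concern.** There are two separate difficulties.

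The first is collection. The outcome needs vital status about three months after the last point at which the protocol provides for any data. A site following the synopsis and section 5.7.2 would not collect it. A site following Table 1 might, at a date of its own choosing. The result could be an outcome that is complete for some participants, absent for others, and measured from different origins.

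The second is attribution. In this cross-over, a participant who completes both cycles has received both policies before the mortality timepoint. A table by strategy needs each death to belong to one strategy, and a death after cycle 2 in such a participant does not. Section 9.3 says the trial is meant to help plan a larger definitive trial, so its mortality data may be read as early safety information on the two policies.

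**Working it through.** **Step 1. The stated duration.** The synopsis gives 18 months of recruitment, an intervention of about 3 months and a trial duration of 2 years.
- Last participant enters at month 18 and finishes at about 18 + 3 = 21 months. Under section 6.8 the trial closes here.
- Three months after that completion: 18 + 3 + 3 = 24 months, which equals the stated 2 years.

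The stated duration therefore has room for a 3-month status check, but the follow-up and closure wording stops about 3 months short of it.

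**Step 2. Who is affected by closure.** If the 3 months run from each participant's own completion, status falls due about 3 + 3 = 6 months after entry. With closure at month 21, anyone entering after month 21 - 6 = 15 reaches that date after the trial has closed. These are the recruits of the last 3 of 18 months. If recruitment were uniform (an assumption; the protocol gives no accrual pattern), that is 36 x 3/18 = 6 participants. Under the synopsis wording, which allows no follow-up after the intervention for anyone, the outcome is unsupported for all participants.

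**Step 3. Whether another provision fills the gap.**
- The 3 Months column in Table 1 could mean 3 months from entry, which is about the end of the intervention, or 3 months after completion. Nothing in the table decides between them.
- Study completion in section 9.2.3 could mean the participant's completion or the trial's.
- Safety reporting does not cover it. The footnote to Table 7a excludes deaths from the underlying disease from SAE reporting. Section 7.2 sends deaths from disease progression to the end of study form, and no form is scheduled three months after completion.

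**Step 4. Attribution by when the death occurs.**

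| Time of death | Strategies received under the trial | Can it be tabulated by strategy? |
|---|---|---|
| Cycle 1 | The allocated one | Yes, as a randomised comparison |
| Cycle 2 | Both, with the second in force | Yes, by strategy in force among those who started cycle 2, with period and carry-over as caveats |
| After cycle 2, both strategies received | Both, neither in force | No, only by sequence or overall |
| After leaving at the end of cycle 1 (for example straight to transplant, section 5.7) | One | Yes |

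Only the third row is a problem. It arises because the definition in section 9.2.3 extends past cycle 2 while section 9.4 asks for a split by strategy. The protocol avoids this for other outcomes: sections 9.2.2 and 9.2.3 cut red cell and platelet units at death or the end of the chemotherapy cycle. Death has no such cut.

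**The case against.** The strongest reply accepts the timepoint conflict but treats it as a drafting lapse. Table 1 does carry a separate Death column after the cycle 2 columns. Section 9.2 draws outcomes from routine records, so a status check needs no visit. The 24-month arithmetic suggests that the check was budgeted, and section 16 says version 2.0 revised section 9 to match the SAP, so other sections may simply not have been updated. This is plausible and makes the fix easy. It does not remove the conflict, because the current text still tells sites that data collection has ended.

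On attribution, the reply is that section 9.4 is labelled brief and gives no window. Its sentence also covers bleeding, which is recorded within cycles, so deaths within a cycle by the strategy in force is a natural reading. That reading is sensible, and the allocation of late deaths could be settled in an SAP. But the split by strategy and the 3-month definition are both fixed in the protocol, and together they do not work for deaths after cycle 2.

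Three stronger readings are tempting and are not supported:
- A reader might infer that late deaths will be counted under whichever strategy came second. No section says so; the protocol gives no assignment rule.
- A reader might infer that the whole mortality table is uninterpretable. It is not, because deaths within a cycle can be tabulated. That a death in cycle 1 leaves no cycle 2 data is inherent in any cross-over and is not an error of this plan.
- A reader might size the problem by applying an assumed mortality to everyone, say 5% to 15% of 36, giving 36 x 0.05 = 1.8 to 36 x 0.15 = 5.4 deaths. The protocol gives no mortality figure, and this counts all deaths, not the subset after cycle 2.

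**Conclusion.** The point holds in two limited parts. First, the mortality timepoint contradicts the synopsis and sections 1.4, 5.7.2 and 6.8, and Table 1 does not resolve it. As written, the outcome has no consistent collection and may be missing for the last participants, although the stated two-year duration could accommodate it. Second, under the only stated definition, deaths after cycle 2 among participants who received both strategies cannot be attributed to one, so the split by strategy in section 9.4 does not work for them.

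The size is modest. Deaths within a cycle are unaffected and the number of affected deaths is unknown. Death is a descriptive clinical outcome here. The primary outcomes and the sample size concern haemoglobin, and progression to a larger trial is judged on adherence of at least 70% in both arms, so none of these changes. The conclusion rests on section 9.2.3 being the definition that section 9.4 uses, since no other is given. It should be corrected because following the text leaves a named outcome uncollected or inconsistently collected.

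**What to change.** **Timepoint.** Choose one of two courses.
- Keep the outcome: state one time origin (for example, each participant's end of cycle 2), and align the synopsis, sections 1.4, 5.7.2, 6.8 and 9.2.3, and Table 1 with it. Say that follow-up after the intervention consists of a vital-status check from records, and that the trial closes once this is done for the last participant.
- Delete the 3-month outcome from section 9.2.3 and the unanchored column from Table 1, and define death within the cycles actually observed.

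**Analysis (section 9.4).** Report:
- deaths from randomisation to the end of cycle 1 by allocated strategy;
- deaths in cycle 2 by the strategy in force, among participants who started cycle 2;
- any later deaths by randomised sequence or overall only.

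**Cost.** Wording changes in the places listed and, if the outcome is kept, a vital-status check from hospital records. The 18 + 3 + 3 = 24 months fit the stated duration, so no extension is needed on the protocol's own timings.
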